#### 4 STUDY DESIGN

The study is a waitlist randomised controlled trial of personalised assessment and intervention for children with conduct and oppositional problems who have not benefitted from parent training, or those who for whatever reason cannot engage in a group approach, compared with no treatment (waiting list). It is a two-centre study conducted from the Tavistock Clinic and the South London and Maudsley NHS Foundation Trust.

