#### 5 METHODS of DATA COLLECTION

Assessments will be conducted on each of the two sites by two Research Assistants. Supervision and assistance will be provided by the Research Coordinator based at the Tavistock Clinic. Assessments will be completed at baseline prior to randomisation and then at 16 and 32 weeks for PPCP and 16, 32 and 48 weeks for PLES. Parents will be sent a link to an online survey (or a paper pack of questionnaires if they prefer) prior to their first meeting with the research assistants and the assistants will support their completion as required. Assessment time points are shown in the flow diagram (see section 4.2 Assessments). The primary end point is 16 weeks after the baseline assessment.

The screen will be the conduct problem sections of the Parent Account of Child symptoms interview, administered by a researcher.

Baseline assessments will include measures on: Demographics, Medical history, Child behaviour including the Primary Outcome Measure (PACS Conduct Section), and Eyberg and SDQ, Co-morbid diagnoses (PACS and SCQ), Child characteristics (ICU and YARC), Parental well-being and parental relationship (GAD-7, PHQ-9), Parenting (Alabama and Self Efficacy). Parents will be asked for their consent for researchers to make an audiovisual recording of parents and children during the Parent/Child observation interaction, and to make an audio recording of the PACS parent interview.

To compensate parents for the time they spend completing questionnaires and being interviewed, we will give them £40 of vouchers for the initial and final assessments, and £10 for completing the interim assessment. We will also refund any travel expenses they might incur as part of the study.

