After it was agreed with the funder to stop recruitment and only formally report on the PPCP vs waitlist comparisons at 16 weeks as part of this study, the SAP had to be amended. Specifically, the proposed analyses were simplified so that they could be carried out after the 16 week data was locked (i.e. not requiring access to any 32 week data:

All analysis will be according to the intention-to-treat principle. Characteristics of the treatment groups will be described at baseline. Preliminary analysis will investigate the pattern of missing outcome

data. The statistical analysis of the primary outcome measure (PACS) and the secondary measures (ECBI etc) will estimate the effect of PPCP relative to waitlist at 16 weeks post randomisation. Briefly, we will use an ANCOVA approach to estimate relevant trial arm differences. The models will contain a dummy variable for the PPCP trial arm and include covariates for binary participant sex and continuous age as known predictors of outcomes and for the randomisation stratifier.

These simplified analyses will remain valid in the presence of missing values in the outcome variables, provided the variables that predict missingness are included in the respective linear mixed model (missing at random, MAR, assumption).

A full statistical analysis plan (SAP) will be developed by the trial statisticians and agreed with the principal investigators and TSC before any post randomisation data is seen by either party.

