#### 8. STUDY SETTING

Potential participants will be identified from the parents or carers of children referred to Parent Training Groups funded and/or delivered by a local authority or NHS at participating sites in North London, South London and Berkshire. Recruitment and data collection will take place at all three sites. Parents who have participated in parent training groups but their children still show high levels of behaviour problems, or those who for whatever reason cannot engage in a group approach will be invited to

take part in the RCT. All CAMHS sites are fully equipped with staff experienced in treating and researching child conduct problems and possess the necessary facilities to conduct this research. For example, all sites have the appropriate rooms for consultations, meetings, individual and group treatment, and suitable toys and books for children.

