#### 9.2 Recruitment

The primary pathway into the trial will be to identify families who have been offered, have attended, or are attending, Parent Training groups being delivered in North London, South London and Oxford for child behaviour problems. Parents who report that their child continues to show challenging behaviour will be targeted. Group facilitators will ask these parents if they would be interested to hear about a research project which is aiming to find out whether a new, individualised approach to child behaviour problems can be more helpful than a group-based approach. Parents will be given a brief introduction to the study and, if they express interest, the facilitator will ask for their permission to pass their contact details on to the study team. Parents who agree to hear more about the study will be contacted by the research team.

Researchers will ask parents to complete a screening questionnaire to determine whether their child's behaviour problems warrant inclusion in the trial. Researchers will also determine that both parent and child fulfil criteria for inclusion into the study, and that there are no criteria that exclude them from taking part. They will establish that the parent has capacity to consent on behalf of both themselves and the child. These parents and children will be invited to take part in the RCT.

A secondary pathway into the trial will be parents of children with significant behaviour problems who are currently in contact with local authorities, the voluntary sector, or CAMHS, who for whatever reason cannot engage in a group approach. They will be invited by their clinician/referrer in the same way as described above.

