# 9.2.2 Randomisation procedures and blinding arrangements

Randomisation of parent/child dyads to waitlist/PLES or PPCP trial arms will be at the individual dyad level with 50% of dyads randomised to either arm. Within parent subpopulation ("decliners" or "non-responders to group approaches") we will use randomly varying block sizes to ensure that the times when dyads start on their allocated groups also balances across trial arms. Randomisation will be provided online vis an independently monitored computer system set up by the accredited Clinical Trials Unit at King's College (KCTU).

The procedure is as follows: Each participant will be allocated a unique, anonymised ID number King's College London Clinical Trials Unit. Details will be entered into the KCLTU randomisation system. The outcome of allocation will be communicated to the trial's senior clinical supervisor, [name], who will then arrange for either a PPCP therapist (intervention arm) or PLES therapist (comparison arm) to make contact with the allocated participant in order to communicate the next steps.

Other members of the research team (including the Chief Investigator, senior statistician and research assistants) will remain blind to participant allocation status throughout the trial. As a result of the change in study design and the analyses of 16-week outcome data before locking the 32 week data collection blinding it is now only possible for the 16-week outcome collection and analyses to remain blind, but not for any 32-week outcome data.

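### Site is in neither the randomisation nor the amended ANCOVA, and the protocol gives conflicting counts and names of sites (minor)

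*Protocol*

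**What the plan says.** **Model.** Section 7.1.1, in the plan adopted after recruitment stopped, analyses PACS and the secondary measures by ANCOVA with a term for the PPCP arm. The models will also "include covariates for binary participant sex and continuous age as known predictors of outcomes and for the randomisation stratifier". The stratifier is singular and site is not listed. The superseded mixed model in the same section did not name site either.

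**Allocation.** Section 9.2.2 randomises individual dyads 1:1. The one stratifier separates families who declined a group from those for whom a group did not work. On blocking inside these strata the section states: "we will use randomly varying block sizes to ensure that the times when dyads start on their allocated groups also balances". No site stratum is mentioned. Research assistants are stated to be blind, and for the 16-week outcome this still applies.

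**Outcome.** The notes on measures in section 4 make the PACS semi-structured interview the primary outcome. Section 5 lists it among the interviews that a researcher holds with the parent.

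**Sites.**
- Section 4: "It is a two-centre study conducted from the Tavistock Clinic and the South London and Maudsley NHS Foundation Trust".
- Section 5: "Assessments will be conducted on each of the two sites by two Research Assistants".
- Section 8: families are identified "at participating sites in North London, South London and Berkshire", and "Recruitment and data collection will take place at all three sites".
- Section 9.2: parent training groups "being delivered in North London, South London and Oxford".

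**The concern.** An interview measure can vary with the team that administers it and with the population it serves. When allocation is not balanced on site, the arms can differ in site mix by chance. In a comparison of about 40 against 40 (section 4.2, Revised Study Plan) such a difference can be noticeable. An ANCOVA without site does not correct for it, and any site variation stays in the residual of an already imprecise comparison. The model adjusts for sex and age because they predict outcome, so it already accepts adjustment for baseline predictors.

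The conflicting site descriptions are a problem in their own right. A site term, a table of recruitment by site and a description of the setting all need one definition of site, and the protocol does not give one.

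**Working it through.** **1. The plan's own figure.** Section 9.2.1 uses 0.4 SD, 80% power, alpha 0.05 (two-sided assumed) and 20% attrition. The formula gives 2 × (1.960 + 0.842)² / 0.4² = 98.1, so 99 per arm and 198 in total; 198 / 0.8 = 247.5, so 248. Both stated figures reproduce, and this point does not change them. The stated 0.16-point difference implies a PACS SD of 0.16 / 0.4 = 0.40.

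**2. Is site carried in indirectly?** The only stratifier in section 9.2.2 is parent subpopulation, and section 7.1.1 adjusts for that one stratifier. Site is therefore absent from both.

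**3. The site descriptions side by side.**

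| Section | Number | Places |
|---|---|---|
| 4 | two centres | Tavistock Clinic; South London and Maudsley |
| 5 | two sites | not named |
| 8 | three sites | North London, South London, Berkshire |
| 9.2 | three areas | North London, South London, Oxford |

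Reading these as two centres with three recruitment areas does not remove the conflict, because section 8 puts data collection as well as recruitment at all three. The third place differs between sections 8 and 9.2.

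**4. Validity with site omitted.** A null effect was simulated with 80 families, two equal sites, individual randomisation and an unadjusted t-test (10,000 runs each). Type I error was 5.1%, 4.7%, 5.4% and 5.0% for site gaps of 0, 0.3, 0.5 and 1.0 SD. There is no inflation.

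**5. Chance imbalance.** Inputs: 80 families, 40 per arm (section 4.2); two sites of 40 (assumption). Let X be the number of PPCP families from the first site. X is hypergeometric with mean 20. A difference of 20 points or more means 24 v 16 or beyond, so P(|X − 20| ≥ 4) = 0.117. A normal approximation without continuity correction gives about 7%; the exact figure is 12%.

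At exactly 20 points, the estimate without site shifts by 0.20 × gap:

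| Assumed site gap | Shift (SD) | Shift (PACS points) |
|---|---|---|
| 0.2 SD | 0.04 | 0.016 |
| 0.3 SD | 0.06 | 0.024 |
| 0.5 SD | 0.10 | 0.040 |

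The standard error at 40 per arm is √(2/40) = 0.22 SD, so the largest of these shifts is under half a standard error.

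**6. Precision.** A gap of g SD between two equal sites explains (g²/4) / (1 + g²/4) of the variance. For g = 0.5 this is 0.0625 / 1.0625 = 5.9%. Adding site multiplies the residual SD by √(1 − R²), but costs one or two degrees of freedom and some correlation between site and arm. Simulation puts that cost at about 0.7% of interval width for two sites and 1.4% for three.

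| R² for site (assumed) | √(1 − R²) | Two sites (× 1.007) | Three sites (× 1.014) |
|---|---|---|---|
| 0 | 1.000 | 0.7% wider | 1.4% wider |
| 5% | 0.975 | 1.8% narrower | 1.1% narrower |
| 5.9% | 0.970 | 2.3% narrower | 1.6% narrower |
| 10% | 0.949 | 4.4% narrower | 3.8% narrower |

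Break-even is at roughly 1.5% (two sites) to 3% (three sites) of variance. Power for 0.4 SD at 40 per arm is 42.4% with site omitted. Counting only the residual SD and the lost degrees of freedom, it rises to 44.1% at R² = 5% and 46.1% at 10%.

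**The case against.** The strongest reply is that the covariate list is a summary. Section 7.1.1 introduces it as brief and defers to a full SAP, which is not shown and may add site. Site was not a stratifier, so leaving it out breaks no rule that the analysis should follow the randomisation. Chance imbalance is already covered by the standard error. All of this stands, and it limits the covariate half to a low-cost improvement to a stated list. It does not settle the conflict over sites, which lies in the protocol's own current text.

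Four stronger readings are tempting, and the documents do not support them.
- *A reader might infer that the PPCP estimate is biased by site.* Individual randomisation, with assessors stated to be blind at 16 weeks, rules this out as a systematic effect, and step 4 shows no inflation of type I error.
- *A reader might take the 0.10 SD shift as the expected error.* It needs a 20-point imbalance (a 12% event at that size or larger) together with an assumed 0.5 SD gap.
- *A reader might assume that sites differ in referral route.* Section 9.2 describes the same pathways without distinguishing sites, and engagement history is already the stratifier.
- *A reader might assume that each interviewer works at one site only.* Section 5 suggests this but does not say it, and one coordinator supervises all of them. If several interviewers share a site, a site term does not remove differences between them.

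Baseline PACS is also absent from the covariate list. That is a separate matter and may count for more in precision.

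**Conclusion.** The point holds as a minor one, in two parts.

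The site descriptions contradict each other on number and on place. This is certain from the text and needs no assumption.

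Site is absent from both allocation and stated model. The consequence is uncorrected chance imbalance and some lost precision, with no loss of validity. The 12% figure assumes two equal sites and 40 families per arm. The 1-2% gain assumes that site explains 5-6% of PACS variance, which is a gap of about 0.5 SD between two equal sites; about 4% needs 10%. The protocol gives no site effect, so these are illustrations. If site explains nothing, adjustment costs 0.7-1.4% of interval width.

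**What to change.** 1. Reconcile sections 4, 5, 8 and 9.2 into one list that separates assessing centres from recruitment areas and settles whether the third area is Berkshire or Oxford. Only the trial team knows which description is correct.
2. Add site as a fixed effect to the section 7.1.1 ANCOVA, for PACS and the secondary measures, before the 16-week data are unblinded. Define it as the centre responsible for the family's baseline assessment. That is fixed before randomisation, whereas the centre doing the 16-week interview is not.
3. Assign any third recruitment area to its baseline assessing centre by a rule written in advance, without reference to observed counts.

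The cost is a change of wording and one or two degrees of freedom. Design, sample size and data collection are unaffected, provided that the baseline assessing centre can be identified for each family. The protocol does not state this, so it should be confirmed.

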## 4.2 Revised Study Plan

In discussion with the funder it was decided to stop recruitment on 31st August 2024 despite not reaching the intended sample size. It was agreed to follow up participants to 16 weeks and then lock these data and analyse only the 16 week outcomes as part of the NIHR funder report. We will formally report on outcome differences between PPCP and waitlist arms at 16 weeks. 32 week outcomes will be collected beyond the end of the original funding period which was 31st April 2025; data will now be collected until 31st August 2025. By necessity future analyses of differences with PLES will not be blind. Depending on attrition rates it might also be only possible to provide descriptive analyses involving the PLES arm. However, the team is committed to ultimately publishing all outcome data collected as part of this study.

By the end of December 2024, we had recorded the outcomes of 80 trial participants at the 16-week-from-randomisation stage. This means that comparisons will be made between 40 participants who have completed the PPCP intervention and 40 participants who have been on the waiting list, which is the primary outcome objective.

[figure not shown]
However, in view of the revised sample size (numbers of participants being around 30-40% of those predicted) the study may be better described as a Pilot and Feasibility Study, rather than a full RCT.

NIHR has agreed a proposal to conduct two additional qualitative interviews exploring the experience of study participants and that of the practitioners in order to optimise learning for the NHS. These will be conducted and analysed as described in Section 7.3 Process Evaluation.

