#### 9.2.1 Size of trial sample

The trial aims to recruit and randomise 248 parent/child dyads. Half of the total number recruited (estimate 124) will be randomised to each arm of the trial. This sample size has been calculated on the basis of a PACS 16 week difference between the mean scores of the PPCP and waitlist groups of 0.4 standard deviations, based on an independent samples t-test with 80% power and alpha=0.05 (sample size required = 198), and is inflated for an anticipated 20% attrition rate (Scott et al 2001; Scott et al 2010). This is a conservative estimate, our previous trial with a clinical population got an effect size of 1.06 standard deviations compared to a wait list control (Scott et al 2001). A standardised effect size of 0.4 amounts to a PACS difference of 0.16 points. We consider such a difference clinically significant because any numerous studies it has been associated with clinically significant reduction in child aggressive and antisocial behaviour, improved school attendance and a happier family atmosphere. Also these improvements have been retained at longer term follow-up over several years (Scott et al 2014).

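### The amended 16-week ANCOVA omits baseline PACS from its listed terms, repeats a missing-data assurance written for a mixed model no longer in the plan, and sits beside a completer description that conflicts with intention-to-treat

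*Protocol*

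**What the plan says.** Protocol section 7.1.1 sets out two plans. In the original one, PACS is analysed in long format by a linear mixed model, with the baseline score stacked as one of the repeated outcomes. In the amended one, "we will use an ANCOVA approach to estimate relevant trial arm differences", using a dummy variable for PPCP plus covariates for sex, age and the randomisation stratifier. Baseline PACS is not listed, although it is collected from every family before randomisation (sections 4.2 Assessments and 5).

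The amended plan opens with "All analysis will be according to the intention-to-treat principle". It ends with a statement on missing data, "These simplified analyses will remain valid in the presence of missing values in the outcome variables, provided the variables that predict missingness are included", and the model in which they are to be included is still called the linear mixed model. The sentence is nearly identical to the one closing the original plan. A preliminary look at the pattern of missing outcomes is planned, and a full SAP is to follow.

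Section 4.2 (Revised Study Plan) reports 80 recorded 16-week outcomes and describes the primary comparison as "40 participants who have completed the PPCP intervention and 40 participants who have been on the waiting list". It does not give the number randomised, and it does not say where families who did not complete PPCP are counted.

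**The concern.** Three statements about the primary analysis do not fit together.

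First, the simplification removed the variable that did most of the missing-data work. With baseline PACS in the stacked outcome, the likelihood allows for loss that depends on baseline severity. With only arm, sex, age and stratum in the model, it does not.

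Second, the validity statement was carried over without being adapted, so a reader is assured about a model that will not be fitted.

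Third, a completion condition on one arm only is not intention-to-treat. Completing PPCP is also not the same as reaching week 16: section 6 lets the number of sessions vary from 12 to 24, while the outcome is timed from randomisation.

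The population makes this more than a formality. Families enter because they declined, dropped out of, did not respond to or could not engage with group training. Section 9.2.1 plans for 20% attrition. Loss that differs between treated and waiting families is plausible.

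**Working it through.** **The plan's own figure.** Inputs from section 9.2.1: "PACS 16 week difference between the mean scores of the PPCP and waitlist groups of 0.4 standard deviations"; "independent samples t-test with 80% power and alpha=0.05 (sample size required = 198"; the total "is inflated for an anticipated 20% attrition rate". Taking alpha as two-sided, n per arm = 2(1.960 + 0.842)² / 0.4² = 98.1, rounded up to 99 (the exact t-test solution is 99.08). Then 2 × 99 = 198 and 198 / 0.80 = 247.5, so 248. Both figures reproduce and nothing below disputes them. The section equates 0.4 SD with 0.16 PACS points, so 1 SD = 0.16 / 0.4 = 0.40 points.

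**Bias from the listed covariates.** Let b be standardised baseline PACS and ρ its correlation with the 16-week score. If loss depends on b, the expected bias of the arm difference without b in the model is

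bias = ρ × [mean of b among observed PPCP − mean of b among observed waitlist].

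The protocol gives neither ρ nor a dropout pattern, so these are assumptions: ρ from 0.3 to 0.7; in PPCP, logit(loss) = −1.6 + b, which gives 20.7% loss; in waitlist, 20% loss unrelated to b. Numerical integration gives a mean b of −0.179 among observed PPCP families and 0 among observed waitlist families. A negative bias favours PPCP.

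| ρ | ρ × (−0.179) | Simulated, no baseline | Simulated, with baseline | Simulated, repeated measures |
|---|---|---|---|---|
| 0.3 | −0.054 | −0.052 | 0.003 | 0.007 |
| 0.5 | −0.089 | −0.094 | −0.005 | −0.007 |
| 0.7 | −0.125 | −0.119 | 0.004 | 0.002 |

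(4,000 simulated trials, 50 per arm, true effect −0.4 SD.) The bias of 0.05 to 0.13 SD is 0.02 to 0.05 PACS points (× 0.40), or 13% to 33% of the 0.4 SD target.

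**When it does not arise.** If loss depends on b equally in both arms, the bracket is zero; simulated bias without baseline was −0.002 to 0.001 SD.

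**Direction.** If milder families leave PPCP instead, the bracket changes sign: +0.179ρ, or +0.05 to +0.13 SD against PPCP. Severity-related loss in the waitlist arm only does the same.

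**What baseline cannot repair.** If loss in PPCP depends on the 16-week score itself, ANCOVA with baseline and the repeated-measures estimator are about equally biased (−0.07 to −0.12 SD).

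**The completer wording taken literally.** PPCP completers against all waitlist, no true effect, completion related to b as above: spurious difference −0.056, −0.097 and −0.126 SD at ρ = 0.3, 0.5 and 0.7; within 0.006 SD of zero with baseline in the model.

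**How many families could be outside the 80.** Section 4.2 puts participants at 30 to 40% of those predicted. If the base is 248, that is 74 to 99, so between none and about 19 randomised families (19/99 = 19%) could lack a 16-week outcome.

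**Precision.** With 40 per arm, the standard error of an unadjusted difference is √(2/40) = 0.224 SD. Adjusting for baseline multiplies it by √(1 − ρ²): 0.213, 0.194 and 0.160 at ρ = 0.3, 0.5 and 0.7.

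**The case against.** The strongest reply has four parts.

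*ANCOVA is valid under MAR given its covariates, and the plan's proviso says so.* This stands. A reader might infer that leaving the mixed model forfeits protection against missing data. It does not: with one follow-up and baseline PACS included, ANCOVA matches the repeated-measures estimator. The proviso could also bring baseline PACS in, if the preliminary analysis found that it predicted loss. But that makes a primary covariate depend on a look at a small dataset, and the assurance is attached to a list without it.

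*Completed is loose wording.* Probably so. The preceding sentence counts recorded outcomes. Recruitment stopped on 31 August 2024, and 16 weeks later is 21 December, which fits the end-of-December count. Assessment is triggered by time, and no completion threshold is defined. A reader might infer a deliberate per-protocol analysis; the protocol does not establish one. The sentence still says something other than intention-to-treat.

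*Bias towards PPCP is not shown.* Correct. Nothing in the protocol supports one direction over the other. Likewise, nothing proposes sessions attended as a covariate; the proviso merely fails to exclude post-randomisation variables.

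*The SAP may settle this, and ANCOVA usually implies baseline adjustment.* Both are possible. But the protocol itself fixes a covariate list and makes a validity claim about it, and those are the statements to correct.

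**Conclusion.** The point holds in limited form. The amended plan's listed covariates omit baseline PACS, its missing-data sentence names a model that is no longer used, and section 4.2 conflicts literally with intention-to-treat.

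The bias from the omission is conditional. It needs loss that depends on baseline severity differently by arm. At about 20% loss in one-arm patterns it reaches 0.05 to 0.13 SD in either direction, roughly a quarter to somewhat over half of the 0.224 SD standard error at 40 per arm (0.05/0.224 = 0.22; 0.13/0.224 = 0.58). The loss model and correlations are assumptions, and realised loss may be anywhere from nil to about 19%.

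The documents do not support saying that ANCOVA is the wrong method, that the estimate is biased in favour of PPCP, or that a completers-only analysis is intended. The reason to act is that including a variable already collected removes a possible bias and gains precision at almost no cost.

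**What to change.** 1. In section 7.1.1, add baseline PACS to the primary ANCOVA, and the baseline value of each secondary outcome to its own model. A two-time-point mixed model (baseline and 16 weeks) would serve equally for missing data.
2. Rewrite the missing-data sentence to name the model actually fitted. State that any covariates added because they predict missingness are baseline variables only. Post-randomisation predictors, if found, enter only as auxiliary variables in an imputation model. Multiple imputation is otherwise optional.
3. In section 4.2, say that all randomised families with a 16-week outcome are analysed in their allocated arm, whatever sessions they attended, and give the numbers randomised and observed in each arm.

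The cost is a few sentences in the protocol, matching text in the SAP, and slightly more analysis work. No new data are needed. The changes should be made before post-randomisation data are seen, the point by which section 7.1.1 requires the SAP to be agreed.
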